APPENDIX 2. FLOW DIAGRAM

CONSORT Diagram

TOMADO: Crossover Randomised Controlled Trial (RCT) of Oral Mandibular Advancement Devices (MAD) for Obstructive Sleep Apnoea-Hypopnoea (OSAH)

APPENDIX 3: RECRUITMENT SCHEDULE

Month	Baseline Ass	Phase 1	Phase 2	Phase 3	Phase 4	Total – new pt	Total – follow-ups	Total episodes	
Month 1	STUDY SET UP								
Month 2	Recruitment and staff training, obtain ethics approval, agree protocols, and initiate trial.								
Month 3	Recrui	tment and st	an training,	obtain etnics	approvai, ag	gree protoco	is, and initiate	uriai.	
Month 4	10					10	0	10	
Month 5	9					9	0	9	
Month 6	10	9				10	9	19	
Month 7	9	8				9	8	17	
Month 8	8	10	8			8	18	26	
Month 9	10	9	8			10	17	27	
Month 10	7	8	10	8		7	26	33	
Month 11	8	9	8	8		8	25	33	
Month 12	10	7	8	9	7	10	31	41	
Month 13	9	7	9	7	8	9	31	40	
Month 14		9	6	8	9		32	32	
Month 15		9	7	8	7		31	31	
Month 16			9	6	6		21	21	
Month 17			8	6	8		22	22	
Month 18				9	5		14	14	
Month 19				8	6		14	14	
Month 20					8		8	8	
Month 21					8		8	8	
Month 22			A 1	NALYSIS &	DEDODTIN	JC.			
Month 23		Fin		HTA, dissem		. ~	nge		
Month 24		1.11	iai report to	IIIA, dissell	illiation of ic	scarch inidi	iigs		
Month 25									
Month 26									
Month 27	LIDDATE) I ITED AT	TIDE CEADA		DI ETION O	ЕПЕУІТІІ	ECONOMIC :	MODEL	
Month 28	UPDATE	LITERAL	UKE SEAK	CII & COMI	LETION U	THEALIH	ECONOMIC .	MODEL	
Month 29									
Month 30									
	90	85	81	77	72	90	315	405	

APPENDIX 4: QUESTIONNAIRES

Epworth Sleepiness Scale

How likely are you to doze off or fall asleep in the following situations, in contrast to feeling just tired? This refers to your usual way of life in the last 4 weeks. Even if you have not done some of these things recently try to work out how they would have affected you. Use the following scale to choose the most appropriate number for each situation:

0	Would never doze
1	Slight chance of dozing
2	Moderate chance of dozing
3	High chance of dozing

Situation	0	1	2	3
Sitting and reading				
Watching TV				
Sitting inactive in a public place (e.g. a theatre or a meeting)				
As a passenger in a car for an hour without a break				
Lying down to rest when circumstances allow				
Sitting and talking to someone				
Sitting quietly after lunch without alcohol				
In a car, while stopped for a few minutes in traffic				

Functional Outcomes of Sleep Questionnaire

Note: In this questionnaire, when the words "sleep" or "tired are used, it describes the feeling that you can't keep your eyes open, your head is droopy, that you want to nod off or that you feel the urge to nap. These words do not refer to the tired or fatigued feeling you may have after you exercised.

FOSQ questions are answered using numbers from 0 to 4 (see answer key below):

- 0= I don't do this activity for other reasons
- 1= Yes, extreme
- 2= Yes, moderate
- 3= Yes, a little,
- 4= No

Please fill out this form completely and select only one answer for each question.

	0	1	2	3	4
Q1) Do you generally have difficulty concentrating on things you do because you are sleepy or tired?					
Q2) Do you generally have difficulty remembering things because you are sleepy or tired?					
Q3) Dou you have difficulty finishing a meal because you become sleepy or tired?					
Q4) Do you have difficulty working on a hobby (for example: sewing, collecting, gardening) because you are sleepy or tired?					
Q5) Do you have difficulty doing work around the house (for example: cleaning house, doing laundry, taking out the trash, repair work) because you are sleep or tired?					
Q6) Do you have difficulty operating a motor vehicle for short distances (less than 100 miles) because you become sleepy or tired?					
Q7) Do you have difficulty operating a motor vehicle for long distances (greater than 100 miles) because you become sleepy or tired?					
Q8) Do you have difficulty getting things done because you are too sleepy or tired to drive or take public transportation?					
Q9) Do you have difficulty take care of financial affairs and doing paperwork (for example: writing checks, paying bills, keeping financial records, filling out tax forms, etc.) because you are sleepy or tired?					
Q10) Do you have difficulty performing employed or volunteer work because you are sleepy or tired?					
Q11) Do you have difficulty maintaining a telephone conversation because you become sleepy or tired?					
Q12) Do you have difficulty visiting with you family or friends in your home because you become sleepy or tired?					
Q13) Do you have difficulty visiting with your family or friends in their homes because you become sleepy or tired?					

Q14) Do you have difficulty doing things for your family or friends because you become sleepy or tired?		
Q15) Has your relationship with family, friends or work colleagues been affected because you are sleepy or tired?		
Q16) Do you have difficulty exercising or participating in a sporting activity because you are too sleepy or tired?		
Q17) Do you have difficulty watching a movie or videotape because you become sleepy or tired?		
Q18) Do you have difficulty enjoying the theater or a lecture because you become sleepy or tired?		
Q19) Do you have difficulty enjoying a concert because you become sleepy or tired?		
Q20) Do you have difficulty watching television because you are sleepy or tired?		
Q21) Do you have difficulty participating in religious services, meeting or a group club because you are sleepy or tired?		
Q22) Do you have difficulty being as active as you want to be in the evening because you are sleepy or tired?		
Q23) Do you have difficulty being as active as you want to be in the morning because you are sleepy or tired?		
Q24) Do you have difficulty being as active as you want to be in the afternoon because you are sleepy or tired?		
Q25) Do you have difficulty keeping a pace with others your own age because you are sleepy or tired?		
Q26) How would you rate yourself in your general level of activity?		
Q27) Has your intimate or sexual relationship been affected because you are sleepy or tired?		
Q28) Has your desire for intimacy or sex been affected because you are sleepy or tired?		
Q29) Has your ability to become sexually aroused been affected because you are sleepy or tired?		
Q30) Has your ability to have an orgasm been affected because you are sleep or tired?		

EuroQol - 5D

[figure not shown]
By placing a tick in one box in each group below, please indicate which statements best describe your own health state today.

Mobility	
I have no problems in walking about	
I have some problems in walking about	
I am confined to bed	
Self-Care	
I have no problems with self-care	
I have some problems washing or dressing myself	
I am unable to wash or dress myself	
Usual Activities (e.g. work, study, housework, family or	
leisure activities)	
I have no problems with performing my usual activities	
I have some problems with performing my usual activities	
I am unable to perform my usual activities	
Pain/Discomfort	
I have no pain or discomfort	
I have moderate pain or discomfort	
I have extreme pain or discomfort	
Anxiety/Depression	
I am not anxious or depressed	
I am moderately anxious or depressed	
I am extremely anxious or depressed	

To help people say how good or bad a health state is, we have drawn a scale (rather like a thermometer) on which the best state you can imagine is marked 100 and the worst state you can imagine is marked 0.

e would like you to indicate on this scale how good or bad your own health is today, in your opinion. Please do this by drawing a line from the box below to whichever point on the scale indicates how good or bad your health state is today.

Your own health state today

SF-36 Health Survey

Instructions for completing the questionnaire: Please answer every question. Some questions may look like others, but each one is different. Please take the time to read and answer each question carefully by filling in the bubble that best represents your response.

1. In general, would you say your h	nealth is:	
Excellent		
Very good		
Good		
Fair Poor		
1 001		
2. Compared to one year ago, how	•	_
Much better now than a ye		
Somewhat better now that About the same as one year		
Somewhat worse now that		
Much worse now than one		
3. The following items are about ac	ctivities you might	t do during a typical day. Does your health now limit you
in these activities? If so, how much		
Vigorous activities, such as running	g, lifting heavy ob	jects, participating in strenuous sports.
Yes, limited a lot.		
Yes, limited a little.		
No, not limited at all.		
	g a table, pushing	a vacuum cleaner, bowling, or playing golf?
Yes, limited a lot.		
Yes, limited a little.		
No, not limited at all.		
Lifting or carrying groceries.		
Yes, limited a lot.		
Yes, limited a little.		
No, not limited at all.		
Climbing several flights of stairs.		
Yes, limited a lot.		
Yes, limited a little.		
No, not limited at all.		
Climbing one flight of stairs.		
Yes, limited a lot.		
Yes, limited a little.		
No, not limited at all.		
Bending, kneeling or stooping.		
Yes, limited a lot.		
Yes, limited a little.		
No, not limited at all.		
Walking more than one mile.		
Yes, limited a lot.		
Yes, limited a little.		

No, not limited at all.	
Walking several blocks. Yes, limited a lot. Yes, limited a little. No, not limited at all.	
Walking one block. Yes, limited a lot. Yes, limited a little. No, not limited at all.	
Bathing or dressing yourself. Yes, limited a lot. Yes, limited a little. No, not limited at all.	
activities as a result of your physic	ou had any of the following problems with your work or other regular daily al health? ou spent on work or other activities?
b. Accomplished less than you wo Yes \square No \square	uld like?
c. Were limited in the kind of world Yes \square No \square	c or other activities
d. Had difficulty performing the w Yes \square No \square	ork or other activities (for example, it took extra time)
	ou had any of the following problems with your work or other regular daily nal problems (such as feeling depressed or anxious)?
a. Cut down the amount of time yo Yes \square No \square	ou spent on work or other activities?
b. Accomplished less than you wo Yes □ No □	uld like
c. Didn't do work or other activitie Yes □ No □	s as carefully as usual
6. During the past 4 weeks, to what normal social activities with family Not at all Slightly Moderately Quite a bit Extremely	t extent has your physical health or emotional problems interfered with your y, friends, neighbours, or groups?
7. How much bodily pain have you None Very mild Mild Moderate Severe Very severe	had during the past 4 weeks? had during the past 4 weeks? had during the past 4 weeks?

	uch did pain interfere with your normal work (including both work outside
the home and housework)? Not at all	
A little bit	
Moderately	
Quite a bit	
Extremely	
	you feel and how things have been with you during the past 4 weeks. For answer that comes closest to the way you have been feeling. How much of
a. did you feel full of pep?	
All of the time	
Most of the time	
A good bit of the time	
Some of the time	
A little of the time	
None of the time	
b. have you been a very nervous pe	erson?
All of the time	
Most of the time	
A good bit of the time	
Some of the time	
A little of the time	
None of the time	
c. have you felt so down in the dur All of the time	nps nothing could cheer you up? □
Most of the time	
A good bit of the time	
Some of the time	
A little of the time	
None of the time	
d. have you felt calm and peaceful	?
All of the time	
Most of the time	
A good bit of the time	
Some of the time	
A little of the time	
None of the time	
e. did you have a lot of energy?	
All of the time	
Most of the time	
A good bit of the time	
Some of the time	
A little of the time	
None of the time	
f. have you felt downhearted and b	vlue?
All of the time	
Most of the time	
A good bit of the time	
Some of the time	
A little of the time	
None of the time	

g. did you feel worn out? All of the time Most of the time A good bit of the time Some of the time A little of the time None of the time	
h have you been a happy person? All of the time Most of the time A good bit of the time Some of the time A little of the time None of the time	
i. did you feel tired? All of the time Most of the time A good bit of the time Some of the time A little of the time None of the time	
10. During the past 4 weeks, how rewith your social activities (like vision All of the time Most of the time Some of the time A little of the time None of the time	nuch of the time has your physical health or emotional problems interfered ting friends, relatives, etc.)?
11. How TRUE or FALSE is each	of the following statements for you?
a. I seem to get sick a little easier the Definitely true Mostly true Don't know Mostly false Definitely false	han other people
b. I am as healthy as anybody I knot Definitely true Mostly true Don't know Mostly false Definitely false	ow
c. I expect my health to get worse Definitely true Mostly true Don't know Mostly false Definitely false	
d. My health is excellent Definitely true Mostly true Don't know Mostly false Definitely false	

Short Calgary Sleep Apnoea Quality of Life Index (SAQLI)

Instructions for completing this questionnaire: Please circle your answer.

We would like to understand whether **your sleep apnoea and/or snoring** have had an impact on your daily activities, emotions, social interactions, and about symptoms that may have resulted.

OVER THE PAST 4 WEEKS:	Not at all	A little	small to moderate	moderate amount	moderate to large	Large	Very large amount
How much have you had to push yourself to remain alert during a typical day (e.g. work, school, childcare, housework)?	7	6	5	4	3	2	1
How often have you had to use all your energy to accomplish your most important activity (e.g. work, school, childcare, housework)?	7	6	5	4	3	2	1
How much difficulty have you had finding the energy to do other activities (e.g. exercise, relaxing activities)?	7	6	5	4	3	2	1
How much difficulty have you had fighting to stay awake?	7	6	5	4	3	2	1
How much of a problem has it been to be told that your snoring is irritating?	7	6	5	4	3	2	1
How much of a problem have frequent conflicts or arguments been?	7	6	5	4	3	2	1
How often have you looked for excuses for being tired?	7	6	5	4	3	2	1
How often have you not wanted to do things with your family and/or friends?	7	6	5	4	3	2	1
How often have you felt depressed, down, or hopeless?	7	6	5	4	3	2	1
How often have you been impatient?	7	6	5	4	3	2	1
How much of a problem has it been to cope with everyday issues?	7	6	5	4	3	2	1
How much of a problem have you had with decreased energy?	7	6	5	4	3	2	1
How much of a problem have you had with fatigue?	7	6	5	4	3	2	1
How much of a problem have you had waking up feeling unrefreshed?	7	6	5	4	3	2	1

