3.9 OUTCOME MEASURES

Schedule: Table 4 summarises outcome measures. Apart from patient preference, all outcomes will be assessed at baseline and at the end of each crossover phase (*i.e.* 5 times in total). See Section 3.7 for the schedule of events.

Primary Outcome:

i. Apnoea-Hypopnoea Index (AHI). AHI is the frequency of apnoeas and hypopneas per hour of study [6].

Respiratory PSG: All participants will undergo respiratory PSG monitoring in their own home using Embletta (Medcare) equipment to determine the AHI at baseline and following each treatment period. The Embletta system is fully compliant with British Thoracic Society and the Association for Respiratory Technology & Physiology recommendations [8] for portable monitoring in OSAH. Its diagnostic signals include body position, pulse oximetry, oronasal flow, nasal pressure, snoring and two respiratory effort signals through XactTrace Respiratory Inductive Plethysmograph (RIP) sensors.

All respiratory PSG studies will be scored manually by a NHS Polysomnographer according to the American Academy of Sleep Medicine (AASM) guidelines [6]. Throughout the study, 5% of studies will be scored in parallel by a second Polysomnographer to ensure inter-rater agreement and adherence to recommended guidelines.

Secondary Outcomes:

- i. Epworth Sleepiness Scale (ESS). Subjective daytime sleepiness is a key feature of OSAH resulting from disrupted sleep. This measure has been included as an important secondary outcome as the effective control of sleepiness is a main aim of treatment.
- ii. Physiological indices from the respiratory PSG 4% Oxygen Desaturation Index, mean, minimum and time <90% of nocturnal SpO2
- iii. Blood Pressure*
- iv. Functional status (Functional Outcome of Sleep Questionnaire, FOSQ)* and Generic (SF-36)
- v. Disease specific HRQoL (Calgary Sleep Apnoea Quality of Life Index, SAQLI)*
- vi. EuroQol EQ-5D transformed to the utility scale*
- vii. Adherence, hours use and retention (assessed by a daily sleep diary)
- viii. Snoring scale* (Partner rated visual analogue scale)
- ix. Health care usage and driving and RTA questionnaire (health economic modeling)
- x. Side effects; withdrawals; and participant satisfaction* and preference*

*Outcome measured for research purposes

MAD Adherence

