5.3 Data Collection

Data will be recorded on a Formic database produced by Papworth R&D department. Formic is a PC software that allows pre-designed questionnaires to be scanned for data-capture and subsequent analysis. The five questionnaires completed by the participants (SF-36, SAQLI, EQ-5D, ESS and FOSQ) will be scanned into Formic whereas all other data will be entered manually from the source data. The following instructions should be followed for the participant questionnaires:

Originals/photocopies

- Do **not** photocopy the forms. Further supplies can be supplied from the Formic office in the R&D department ([name]).
- The forms should be completed in black or blue ink.

Initials/Characters

- Patient initials must be written in upper case letters.
- If there are only two initials, complete the first and third boxes and put a dash in the second box.
- The initials for a patient must be in the same format on all the forms throughout the study.

Errors

- If an error is made when answering yes/no boxes, fill the box in completely and place an **X** in the correct box.
- If an incorrect entry is made in a box which needs to be amended e.g. a date box, cross out the incorrect entry and enter the correct response in the box or write the answer as close to the outside of the box as possible.
- If there are multiple errors on the same page it is advisable to complete a new form.
- All corrections made by trial staff should be initialed and dated and explained, if necessary (Ref. ICH/GCP 4.9.3).

Free Text

Free text cannot be scanned but is analysed separately

Incomplete Data

Ensure that all sections of the forms are completed or that an explanatory comment is added

6. Outcome Measure Analysis

Primary outcome measure

A NHS Polysomnographer independent of the research team and thus who is blinded to treatment allocation will analyse respiratory PSG studies in order to calculate AHI.

Secondary outcome measures

Secondary outcomes will be administered by the CRA on pre-prepared CRFs. Participants cannot be blinded as they are likely to be aware or will be able to divulge which device they are using.

7. Statistical Analysis

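### The FOSQ form in Appendix 4 applies one yes/no answer key to all 30 items, leaving item 26, a rating of activity level, without a defined meaning

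*Protocol*

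**What the plan says.** Section 3.9 of the protocol lists the questionnaire among the secondary outcomes: "Functional status (Functional Outcome of Sleep Questionnaire, FOSQ)* and Generic (SF-36". Table 5 in Section 3.10 schedules it at baseline, at the end of each of the four crossover phases, and at follow-up years 1 and 2. Section 5.3 states that the five participant questionnaires, the FOSQ among them, are scanned into the Formic database.

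Appendix 4 reproduces the form. It opens with "FOSQ questions are answered using numbers from 0 to 4 (see answer key below". The lowest code is "0= I don't do this activity for other reasons". Codes 1, 2 and 3 are a yes graded as extreme, moderate and a little, and code 4 is a plain no. Participants are told: "Please fill out this form completely and select only one answer for each question". No item is exempted from either instruction, and no second key is visible.

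Item 26 is "Q26) How would you rate yourself in your general level of activity". The items on either side are "Q25) Do you have difficulty keeping a pace with others your own age because you are sleepy or tired" and "Q27) Has your intimate or sexual relationship been affected because you are sleepy or tired".

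**The concern.** The key is built for questions about difficulty or impairment, where a no is the best answer and earns the highest code. Item 26 is not such a question. It asks the participant to rate a level, it does not mention sleepiness, and neither a no nor any grade of yes answers it. A participant who follows the instructions must still tick one box.

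What that tick means is then left to the participant. Someone who is very active and picks the nearest-sounding word, extreme, receives code 1, which on every other item marks the worst function. At stake is the interpretability of one component of the functional-status outcome. If some participants read the item that way, a real improvement in activity on a device would lower their item score. If a participant reads it differently from one period to the next, noise is added to the treatment contrasts.

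**Working it through.** The protocol gives no FOSQ figure to reproduce, so the main check compares items with key.

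**Step 1: fit of each item to the key (Appendix 4).**
- Items asking whether there is difficulty: 1 to 14 and 16 to 25, that is 14 + 10 = 24.
- Items asking whether something has been affected: 15 and 27 to 30, that is 1 + 4 = 5.
- Items asking for a rating of a level: 26 only.
- Total 24 + 5 + 1 = 30. For 29 items a graded yes or a no is a natural answer and 4 is the best state. Item 26 is the only one that does not fit.

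**Step 2: item error if extreme is read as very active.** Let the true activity level be a, from 1 (low) to 4 (high), intended to be coded so that 4 is best. Under this reading the recorded code is 5 − a, and the error is (5 − a) − a = 5 − 2a.

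| True level a | Recorded 5 − a | Error |
|---|---|---|
| 1 | 4 | +3 |
| 2 | 3 | +1 |
| 3 | 2 | −1 |
| 4 | 1 | −3 |

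The largest error at one assessment is 3 points.

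**Step 3: what this does to a within-participant contrast.** If the participant reads the item this way throughout and activity does not change, the recorded difference is 0, as it should be. If activity changes by d, the recorded change is (5 − a − d) − (5 − a) = −d, so the sign is wrong. For example, a move from level 2 to level 4 is recorded as 3 to 1, a change of −2 instead of +2.

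**Step 4: effect on a score.** The protocol states no scoring rule or subscales, so these are illustrations under assumptions.
- Simple sum of 30 items using codes 1 to 4 and leaving out code 0: range 30 to 120, width 90. The largest single-assessment error is 3/90 = 3.3% of that width.
- Mean over 30 items: 3/30 = 0.10.
- Mean over a subscale containing item 26, with an assumed size of 5 to 9 items: 3/5 = 0.60 down to 3/9 = 0.33.

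**The case against.** A reader might go further and infer that item 26 is in fact reversed in the FOSQ score and that nothing later corrects it. The documents do not support that, for four reasons.

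1. **Reversal needs a particular reading.** The form tells participants to answer with numbers, and a participant who ignores the labels and rates activity from low to high would place high activity at 4. Items 22 to 25 concern difficulty being active or keeping pace, so someone who reads item 26 as continuing that series would also use 4 for the best state. Nothing in the protocol shows which reading prevails.
2. **Scoring is not described.** The protocol gives no FOSQ scoring rule. That is commonly left to the SAP, which was not available, or to the instrument's manual. Scanning is data capture and does not exclude later recoding.
3. **Appendix 4 may not be the form in use.** Section 5.3 refers to pre-designed Formic forms and gives rules for initials boxes, which the appendix copy of the FOSQ does not show.
4. **The answer grid could not be read in full.** In the extracted text the answer cells are incomplete from item 14 onward, so a separate set of labels beside item 26 cannot be wholly excluded.

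These points stand. They rule out any claim that the score is known to be reversed, and any blanket instruction to discard item 26, which would throw away a valid item if the live form was labelled properly. They do not remove the mismatch itself. The key, the instruction to answer every item and the wording of item 26 are all intact, and together they give the response no defined meaning. A scoring rule cannot recover what a participant meant by a moderate yes to this item.

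**Conclusion.** The point holds as a minor defect in the printed form: one of 30 items is paired with a key that does not answer it. What is established is that an item 26 response under that key is uninterpretable. That it runs against the rest of the scale is a possibility only.

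The size is small even in the worst case worked above. A stable reading also cancels between a participant's periods when activity is unchanged. The FOSQ is one of many secondary outcomes, and AHI, the primary, is unaffected. The conclusion assumes that Appendix 4 reflects the form participants complete. The conversion to a score further assumes equal item weights, and the subscale range assumes 5 to 9 items, because the protocol fixes neither. The point deserves attention mainly because checking and repairing it is nearly free.

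**What to change.** First, compare the FOSQ form in use in Formic with Appendix 4. If item 26 already has suitable responses there, correct the appendix and do nothing more.

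If item 26 carries the shared key, print it with its own activity-level responses, ordered from low to high and coded so that 4 is best, as on the other items.

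Only if completed forms are confirmed to have used the shared key, compute the FOSQ without item 26 and report the score including it as a sensitivity analysis. Apply the same rule to all of a participant's assessments, so that treatment contrasts do not mix two versions of the score.

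The cost is one check of a form, one changed line if needed, and one scoring rule. No extra data collection is involved.
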